## 6.7 Examination of Subgroups

Subset analysis by age group (adolescents and adults) will be conducted for both safety and efficacy data. Subset analysis by vIGA-AD strata (“2” (mild) and “3” (moderate)) will also be conducted on the primary and secondary efficacy endpoints. Details on these analyses are described in Sections 12.1, 12.2, and 13.

# 7 STUDY SUBJECTS

---

## 7.1 Disposition of Subjects

All subjects who provide informed consent will be accounted for in this study. The number of subjects screened and subjects rescreened will be presented. Screen failures and the reason for screen failure will be presented for all screened subjects except for those who were rescreened and did not fail the second screening. Moreover, the number of subjects randomized and included in each analysis population will be presented. Study completion status and the reason for study discontinuation will also be presented. The percentage of subjects with screen failures will be calculated using the number of subjects screened as denominator. The percentage of screen failure by reasons will be calculated using the number of screen failures as denominator. The percentage of subjects with study discontinuation will be calculated by reasons using the number of subjects who did not complete study as denominator. Otherwise, percentages will be calculated using the number of subjects randomized as denominator. Number of days in the study will be calculated as follows and summarized:

$$\text{Number of days in study} = \text{Date of completion/discontinuation} - \text{1}^{\text{st}} \text{ dose date} + 1$$

A listing of subject’s disposition will be provided. Information on first screening for subjects who were rescreened, including the rescreened subject identifier, will be presented under the first screening subject identifier. A listing of subject’s randomization information and a listing of subjects included in each of the study populations will also be provided.

## 7.2 Protocol Deviations

The number of events and the number and percentage of subjects with at least one major protocol deviation will be summarized by deviation category using the safety population. A listing of all

 INNOVADERM RESEARCH INC.	STATISTICAL ANALYSIS PLAN, Final V1.0Final 1.0
Protocol Number: AQR-151-212	Sponsor: Arcutis, Inc.

protocol deviations will also be provided. The number of events and the number and percentage of subjects with at least one important protocol deviation will be summarized by deviation category using the safety population. A listing of subjects with inclusion and exclusion criteria deviations will also be provided. This listing will identify important and major protocol deviations.

An important protocol deviation is a deviation that might significantly affect the completeness, accuracy, and/or reliability of the study data or that might significantly affect a subject's rights, safety, or well-being. A major protocol deviation is a deviation that is likely to affect the primary efficacy data (Total EASI score).

## **8 DEMOGRAPHIC AND OTHER BASELINE CHARACTERISTICS**

---

Demographics and baseline characteristics will be summarized with descriptive statistics using the safety population. The list of demographics and baseline characteristics to be summarized will include:

- Age (years) – calculated relative to date of consent
- Sex
- Ethnicity
- Race
- Baseline Height (cm)
- Baseline Weight (kg)
- Baseline EASI
- Baseline vIGA-AD
- Baseline BSA Involvement
- WI-NRS Pruritus Score

A listing of all demographics and baseline characteristics will be provided.

 INNOVADERM RESEARCH INC.	STATISTICAL ANALYSIS PLAN, Final V1.0Final 1.0
Protocol Number: AQR-151-212	Sponsor: Arcutis, Inc.

## 9 SURGICAL AND MEDICAL HISTORY

---

Surgical and Medical history will be coded according to the Medical Dictionary for Regulatory Activities (MedDRA), Version 22.0.

Surgical and medical history will be summarized by system organ class (SOC) and preferred term (PT) using the safety population. A subject who experienced the same surgical and medical history event multiple times will be counted only once for the corresponding PT. Similarly, if a subject experienced multiple surgical and medical history events within the same SOC, the subject will be counted only once for that SOC. Surgical and medical history events will be sorted alphabetically by SOC and within each SOC the PT will be presented by decreasing order.

A listing of all surgical and medical history events will be provided.

## 10 PRIOR AND CONCOMITANT MEDICATIONS

---

Medications will be coded according to the World Health Organization Drug Dictionary (WHO-DD), GLOBAL B3 March 1, 2019.

Prior medications are defined as any medication started and discontinued prior to the first study treatment dose. Concomitant medications are defined as any medication taken after the first study treatment dose, including those starting prior to the first study treatment date and continuing past that date. See [Appendix 2](#) for handling of completely or partially missing dates for prior and concomitant medications.

Incidence of prior and concomitant medications will be tabulated by anatomical therapeutic chemical (ATC) level 3 and PT using the safety population. A subject with the same medication taken multiple times will be counted only once for the corresponding PT. Similarly, if a subject has taken more than one medication within the same ATC level, then the subject will be counted only once for that ATC. Prior and concomitant medications will be sorted alphabetically by ATC level and within each ATC level the PT will be presented by decreasing order.

A listing of all prior and concomitant medications will be provided.

 INNOVADERM RESEARCH INC.	STATISTICAL ANALYSIS PLAN, Final V1.0Final 1.0
Protocol Number: AQR-151-212	Sponsor: Arcutis, Inc.

## 11 STUDY TREATMENT EXPOSURE AND TREATMENT COMPLIANCE

---

A summary of exposure related to ARQ-151 cream and the vehicle will be presented using the safety population. It will include descriptive statistics on the number of days treated, as well as the number of treatment applications, for each treatment group.

For each treatment, compliance will be calculated as follows:

$$\frac{\text{Number of treatment applications}}{\text{Number of expected treatment applications}} \times 100$$

Since the study treatment is applied once daily, the number of expected treatment applications is 28 for all subjects. Descriptive statistics for the compliance as well as the number of missed applications, subjects with  $< 80\%$  and  $\geq 80\%$  compliance will be presented by treatment. Furthermore, the incidence of subjects who missed more than 3 consecutive doses and compliant subjects will be presented by treatment.

A subject will be considered compliant with the dosing regimen if the subject applies at least 80% of the expected applications during the study drug application period and does not miss more than 3 consecutive doses.

Exposure and compliance, including compliance collected at each clinic visit, will be displayed in a listing of study treatment administration by subject, for each treatment. A listing of drug accountability including the tube number, dispensed and returned weight will also be provided.

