5 SCHEDULE OF VISITS AND ASSESSMENTS

STUDY EVENTS FLOW CHART:

Study Procedure	Screen	Baseline Day 1	Day 2, 24-hour PK Collection	Wk 1 Day 8	Wk 2 Day 15	Day 16, 24-hour PK Collection	Wk 4 Day 29
Visit	1	2	3	4	5	6	7
Visit Window	-4 weeks			+/- 3 days	+/- 3 days		+/- 3 days
Informed consent	X						
Demographics	X						
Medical and surgical history	X						
Physical examination ^a	X	X					X
I/E criteria	X	X					
Hematology, Serum Chemistries, and Urine Analysis	X	X					X
12 lead ECG	X						X
Vital signs, height, weight ^b	X	X		X	X		X
vIGA-AD ^c , EASI ^c , BSA ^c	X	X		X	X		X
WI-NRS pruritus ^d	X	X		X	X		X
Local Tolerability Assessment ^e		X		X	X		X
PHQ-8, C-SSRS	X	X		X	X		X
Optional photography ^f		X		X			X
Serum pregnancy test	X						
Urine pregnancy test ^g		X		X	X		X
PK draws ^h		X	X		X	X	X
Drug/vehicle application in clinic ⁱ		X		X	X		
Dispense study medication kit ^j		X		X	X		
Dispense/review diary		X		X ^o	X		X ⁿ
Weigh study medication kit ^k		X		X	X		X
Compliance calculation ^l		X		X	X		X
Adverse event assessment ^m	X	X	X	X	X	X	X
Concomitant medications	X	X		X	X		X

^a Limited physical examination: skin, lungs, and heart only

^b Height will be collected at Screening only. Weight will be collected at all study visits. Subject to void prior to weight being taken. Remove any jackets, outerwear and shoes. Remove any objects of significant weight (i.e. cell phones, wallet, key chains). A 5% weight loss should be reported to the medical monitor.

^c vIGA-AD will be a 5-point scale ranging from clear (0) to severe (4) and is evaluated for the entire body except the scalp, palms, and soles. EASI takes into account overall severity of erythema, infiltration/papulation, excoriation, and lichenification, in addition to extent of BSA affected. The 4 clinical signs will be graded on a 4-point scale (0 [absent] to 3 [severe]) for 4 body regions (head and neck, upper extremities, lower extremities, and trunk). Total EASI score will be calculated as a sum of scores of all 4 body regions. EASI total score will range from 0 (absent) to 72 (severe). Total BSA

affected by AD will be determined for all body surfaces except the scalp, palms and soles. vIGA-AD should be completed prior to other physician assessments.

- ^d Subjects will complete the WI-NRS pruritus questionnaire.

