- ^e Local tolerability assessments should be recorded prior to study drug application for the Investigator assessment of skin irritation (Berger and Bowman skin irritation score) and 10-15 minutes post-drug application for the subject's '0-3' burning/stinging assessment.
- ^f Photography of AD lesion(s) selected by the Investigator will be performed at some investigational sites. Photography will be optional. All efforts will be made to de-identify the subjects.
- ^g A urine pregnancy test will be administered to all females of child-bearing potential. A negative result is required for continued participation in the study, and results must be available prior to dispensing of study drug at each visit.
- ^h For the subset of subjects who enrolled under the previous amendment and agreed to the serial PK: on the first day of dosing, PK draws will be done pre-dose (within 1-hour) and at 1, 2, 4, 6 (all \pm 20 min) and 24 hours (\pm 2 hr) post-dose administration. On Day 15, PK draws will be taken at pre-dose (within 1-hour), 1, 2, 4, 6 (all \pm 20 min) and 24 hours (\pm 2 hr) post dose administration. For other subjects: PK draws will be collected at Days 1 and 29. The draws will be pre-dose, \leq 60 minutes before drug application in the clinic. Ensure study medication is not applied in the area where PK will be drawn.
Note: Day 2 and Day 16 visits for 24-hour PK collection only apply to the subset of subjects who agree to the serial PK.
- ⁱ Subjects to apply assigned IP in clinic at every visit.
- ^j Kits will be dispensed based on %BSA affected. See IP Handling Manual for details.
- ^k The entire kit should be weighed and recorded at every visit. See IP Handling Manual for details.
- ^l Compliance calculation is described in the IP Handling Manual
- ^m Any emergent AEs will be followed in the clinic for up to one month at the Investigator's discretion until resolved or otherwise judged as clinically stable.
- ⁿ On Day 29, no further IP will be applied or dispensed.
- ^o On Day 8, dispensing of IP is optional. Site should review IP kit to ensure sufficient IP is available until the next visit and only dispense additional IP if needed.

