9.10.2 Treatment Administration

At the randomization visit (Baseline visit), the study staff will demonstrate to the subject how to apply ARQ-151 cream or vehicle cream using the first tube from the kit that is assigned to the subject at randomization. Study site staff will be trained to ensure a unit dose (a pea size unit of ARQ-151 vehicle cream will cover approximately 1% BSA) is properly squeezed from the tube and applied to atopic dermatitis lesion(s) as a thin film and rubbed in using the index and middle finger, rubbing in thoroughly but gently, until the 'white' has disappeared. The subject will then practice squeezing a similar amount onto their index and middle finger and apply a thin film to other areas to be treated. The study staff will confirm that the subject's application technique is correct.

Re-training will be conducted at subsequent visits as needed (i.e., if the returned tube(s) weighs substantially different than the expected weight).

Subjects will be instructed to apply study medication once daily to all treatment areas identified by the investigator at Baseline using a Body Diagram (see [Appendix 1](#)).

Note:

- All subjects should apply medication each evening (except on clinic visit days) at least 15 minutes after showering or bathing (if they take an evening shower/bath) and then not wash areas where ARQ-151 cream or vehicle has been applied until at least 4 hours after study drug application and preferably not until the following morning. Study medication should be applied at least 20 minutes before going to bed.
- Subjects should maintain treatment of areas with study drug for the duration of the study regardless of whether treatable areas of AD clear prior to Day 29.
- New lesions that develop during the study should be treated (except scalp). An unscheduled visit is not required for starting treatment of new lesions.

Each study medication tube will be weighed prior to dispensing at the baseline visit or subsequent visits. Study medication tubes must be returned by subjects at each study visit, both empty and full, and will be weighed. If the subject's actual use is substantially different than the expected use for the subject's BSA (see IP Handling Plan), the subject will be retrained on the study drug application technique.

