9.10.3 Treatment Compliance

Study medication tubes will be weighed at each follow-up clinic visit.

Subjects will complete a daily diary recording the date and time of each dose applied, any missed doses, and a comment section should the subjects have a comment, e.g., record potential AEs. Site personnel will review the diaries and use the information to question the subject regarding compliance and AEs and then record appropriate information in source documents and complete Case Report Forms (CRFs). If a subject misses a dose, they should be instructed to return to the protocol study medication administration schedule (i.e. if subject forgets a dose they should wait until that evening and apply as usual).

A subject will be considered compliant with the dosing regimen if the subject applies at least 80% of the expected applications during the study drug application period and does not miss more than 3 consecutive doses.

Compliance will be assessed by review of the dosing diary. Weight of study medication applied will be measured for reporting purposes.

If the diary shows less than 80% of expected use, the subject is using too little study drug and retraining must be conducted and documented.

Compliance will be documented in source and in eCRF.

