10.4 Final Study Visit

The approximate final study visit will occur at Week 4 (Day 29). The procedures performed during these visits are as described in Schedule of Events ([Section 5](#)). A 3-day scheduling leeway period is allowed for this visit.

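### A fixed denominator of 28 applications scores some completers with a permitted early Week 4 visit below 80% and removes them from the supportive per-protocol population

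*SAP*

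**What the plan says.** SAP section 11 defines compliance as the number of applications divided by the number expected, times 100. Because dosing is once daily, it adds that "the number of expected treatment applications is 28 for all subjects". The same section, and Protocol 9.10.3, call a subject compliant who "applies at least 80% of the expected applications during the study drug application period and does not miss more than 3 consecutive doses". SAP 4.2 repeats both parts of that rule as conditions for the per-protocol (PP) population. SAP 11 also tabulates subjects below and at or above 80% by treatment.

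The passages that fix how many doses a completer can take are these:

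- **Visit window.** Protocol 10.4 says of the Week 4 visit: "A 3-day scheduling leeway period is allowed for this visit". The schedule in Protocol section 5 gives Day 29 plus or minus 3 days, that is Day 26 to Day 32.
- **Dosing at the final visit.** In that schedule the row "Drug/vehicle application in clinic" is blank at Week 4, and footnote n reads: "On Day 29, no further IP will be applied or dispensed". Footnote i, attached to the same row, reads: "Subjects to apply assigned IP in clinic at every visit".
- **Return of product.** Protocol 9.10.2: "Study medication tubes must be returned by subjects at each study visit, both empty and full, and will be weighed".
- **Other source.** Footnote l says: "Compliance calculation is described in the IP Handling Manual". That manual is not among the documents.

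**The concern.** The figure of 28 is the dose count for a subject seen exactly on Day 29 with no dose that day. A visit on Day 26, 27 or 28 is within the window and is not a deviation, but it ends the application period 3, 2 or 1 doses sooner. The fixed denominator counts those unavailable doses as missed. This conflicts with the rule's own reference to the study drug application period. The protocol's definition contains no fixed 28, and SAP 3.5 does not list the figure as a change from the protocol.

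At stake are PP membership and the by-treatment compliance table. A completer who missed a few doses could be kept in or left out of PP solely because of the day on which a permitted visit was booked.

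**Working it through.** **Inputs.** Once-daily dosing from Day 1 (Protocol 9.10.2); Week 4 visit on Day 26 to 32 (Protocol sections 5 and 10.4); denominator 28 (SAP 11); threshold 80% and no more than 3 consecutive missed doses (Protocol 9.10.3, SAP 4.2 and 11).

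**The plan's own figure.** Day 1 to Day 28, with none on Day 29, gives 4 × 7 = 28. This reproduces.

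**Fixed cut-off.** 0.80 × 28 = 22.4, so 23 applications are needed whatever the visit day: 23/28 = 82.1% passes and 22/28 = 78.6% fails.

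**Cut-off on available doses, with no dose at the final visit (footnote n).** For visit day d, available = d − 1 and needed = 0.80 × (d − 1), rounded up.

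| Visit day | Available | Needed for 80% | Needed under fixed 28 | Misclassified |
|---|---|---|---|---|
| 26 | 25 | 20 | 23 | 20, 21, 22 fail (80.0, 84.0, 88.0% scored as 71.4, 75.0, 78.6%) |
| 27 | 26 | 21 | 23 | 21, 22 fail (80.8, 84.6% scored as 75.0, 78.6%) |
| 28 | 27 | 22 | 23 | 22 fails (81.5% scored as 78.6%) |
| 29 | 28 | 23 | 23 | none |
| 30 | 29 | 24 | 23 | 23 passes (79.3% scored as 82.1%) |
| 31 | 30 | 24 | 23 | 23 passes (76.7% scored as 82.1%) |
| 32 | 31 | 25 | 23 | 23, 24 pass (74.2, 77.4% scored as 82.1, 85.7%) |

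The last three rows apply only if dosing continues to a late visit, which the documents do not settle. The subjects who wrongly fail missed 3 to 5 doses and can still satisfy the limit on consecutive misses. Perfect use by a completer seen on Day 26 scores 25/28 = 89.3%, so it passes.

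**Other reading, with a dose at the final visit (footnote i).** Available = d. Day 26: 21–22 of 26 wrongly fail. Day 27: 22 of 27 wrongly fails. Day 28: no error. Day 29: 29 are due and 24 needed, so 23 wrongly passes. Neither reading makes 28 right for every permitted visit day.

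**How many subjects.** The documents give no adherence or visit-day data, so what follows is assumption only. Each day's dose is taken independently with probability p. The wrongly failed share is P(needed ≤ X ≤ 22 and no run of more than 3 misses), where X is binomial on the available doses, computed by exact recursion. With no dose at the final visit:

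| p | Day 26 | Day 27 | Day 28 | (a) visits even over Day 26–32 | (b) 5% on each of Days 26, 27, 28 |
|---|---|---|---|---|---|
| 0.85 | 58.3% | 37.5% | 17.1% | 16.1% | 5.6% |
| 0.90 | 42.9% | 21.8% | 7.9% | 10.4% | 3.6% |
| 0.95 | 12.6% | 3.7% | 0.8% | 2.4% | 0.9% |
| 0.97 | 3.8% | 0.7% | 0.1% | 0.7% | 0.2% |
| 0.98 | 1.3% | 0.2% | 0.02% | 0.2% | 0.08% |
| 0.99 | 0.2% | 0.01% | 0.001% | 0.03% | 0.01% |

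Column (a) is the sum of the three day columns divided by 7; column (b) is that sum times 0.05. If all 105 subjects complete, (a) is about 17, 2.6 and 0.03 subjects at p = 0.85, 0.95 and 0.99, and (b) is about 5.9, 0.9 and 0.01. With a dose at the final visit and an even spread, the shares are 7.8, 4.2, 0.6, 0.1, 0.03 and 0.002% down the same rows.

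**The case against.** The strongest reply is that treatment is planned as 4 weeks once daily, and scoring everyone against the planned course is a recognised convention. On that view a subject with 20 applications received 71% of the course and may reasonably be left out of PP. This stands for early leavers, and the SAP could say so. For completers it conflicts with the SAP's own wording, which ties the 80% to the application period.

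SAP 4.2 does not cite SAP 11, and a separate compliance figure is collected at each visit under a manual we have not seen. The link to PP is therefore an inference. It is a strong one: SAP 4.2 repeats the two-part rule in SAP 11, which holds the only formula in either document and states 28 outright.

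Footnote i may be loose wording, since its row is marked only at Baseline, Week 1 and Week 2. Even so, misclassification at Days 26 to 28 under footnote n does not depend on it.

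The upper figure of 17 subjects needs low adherence, evenly spread visits and no dropout together. With the plan's 10–25% dropout, 105 becomes about 79 to 94 completers and 16.1% of these is about 13 to 15. Under the same assumptions (p = 0.85, even spread), about 4.9% would wrongly pass if dosing runs to Days 30–32. About 24% of subjects seen exactly on Day 29 would also fail at p = 0.85, and rightly so. These points limit the size but do not remove the error.

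SAP 11 also reports days treated, number of applications, missed applications and runs of more than 3 misses, and SAP 7.1 reports completion status and days in study. Only the compliance percentage and what hangs on it are affected.

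**Conclusion.** The concern holds and is minor. A fixed 28 wrongly fails completers with 20–22 of 25, 21–22 of 26 or 22 of 27 doses when no dose is given at the final visit, and those with 21–22 of 26 or 22 of 27 when one is. These cut-offs are exact and need no assumption beyond once-daily dosing from Day 1. The share of subjects is unknown; the rates above rest on assumed independent daily adherence and assumed visit timing, and are very small once adherence is 97% or more with visits clustered on Day 29. The effect is confined to the compliance tables and the supportive PP analysis. The ITT primary analysis, its alpha and its power do not change.

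**What to change.** Before database lock:

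1. In SAP 11, define expected applications for completers as the once-daily doses due from first application to the day before the actual Week 4 visit, or to the visit day if the sponsor reconciles footnotes i and n that way. Say that this number is used for the 80% rule in SAP 4.2. State also how doses are counted when the visit falls on Day 30 to 32.
2. For early leavers, either keep the planned 28 and say so, or use doses due to discontinuation. The second option needs an explicit minimum-exposure or Week 4 assessment criterion in SAP 4.2; without one, a subject who left on Day 8 with 7 of 7 doses would enter PP.
3. Reconcile footnotes i and n of the schedule.

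The cost is one derivation change and one added statement or criterion. Visit dates and diary counts are already collected. The drawback is that compliance is no longer measured against one common planned course, so the tables need a footnote on the denominator.
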